5.2. Prohibited Medications and Measures

- Use of any concurrent anticancer therapy (eg, chemotherapy, radiation therapy, surgery, immunotherapy, biologic therapy, hormonal therapy, or tumor embolization) other than those specified in the Protocol.
- Concomitant use of a JAK inhibitor
 - Concomitant use of immunosuppressive therapies
 - Live vaccines during the study and up to 3 months following the last dose of itacitinib
- Use of any investigational medication within 28 days or 5 half-lives, whichever is longer, prior to the first dose of study drug through the duration of study treatment is prohibited.
- St John's wort and rifampin are not permitted at any time during study participation.

6 ADVERSE EVENTS

6.1 Definitions

Adverse Event (AE): any untoward medical occurrence in a patient or clinical trial subject administered a medicinal product and which does not necessarily have a causal relationship with this treatment. *An AE can therefore be any unfavourable and unintended sign (including an abnormal laboratory finding), symptom, or disease temporally associated with the use of an investigational medicinal product (IMP), whether or not considered related to the IMP*

Adverse Reaction (AR): all untoward and unintended responses to an IMP related to any dose administered. *All AEs judged by either the reporting investigator or the sponsor as having reasonable causal relationship to a medicinal product qualify as adverse reactions. The expression reasonable causal relationship means to convey in general that there is evidence or argument to suggest a causal relationship.*

Unexpected Adverse Reaction: an AR, the nature or severity of which is not consistent with the applicable product information (eg investigator's brochure for an unapproved investigational product or summary of product characteristics (SmPC) for an authorised product). *When the outcome of the adverse reaction is not*

consistent with the applicable product information this adverse reaction should be considered as unexpected. Side effects documented in the SmPC which occur in a more severe form than anticipated are also considered to be unexpected.

Serious Adverse Event (SAE) or Serious Adverse Reaction: any untoward medical occurrence or effect that at any dose:

- **Results in death.**
- **Is life-threatening** – *refers to an event in which the subject was at risk of death at the time of the event; it does not refer to an event which hypothetically might have caused death if it were more severe.*
- **Requires hospitalisation, or prolongation of existing inpatients' hospitalisation.**
- **Results in persistent or significant disability or incapacity.**
- **Is a congenital anomaly or birth defect**

Medical judgement should be exercised in deciding whether an AE/AR is serious in other situations. Important AE/ARs that are not immediately life-threatening or do not result in death or hospitalisation but may jeopardise the subject or may require intervention to prevent one of the other outcomes listed in the definition above, should also be considered serious.

Suspected Unexpected Serious Adverse Reaction (SUSAR): any suspected adverse reaction related to an IMP that is both unexpected and serious.

6.2 Causality

Most adverse events and adverse drug reactions that occur in this study, whether they are serious or not, will be expected treatment-related toxicities due to the drugs used in this study. The assignment of the causality should be made by the investigator responsible for the care of the participant using the definitions in the table below.

If any doubt about the causality exists the local investigator should inform the study coordination centre who will notify the Chief Investigators. The pharmaceutical companies and/or other clinicians may be asked to advise in some cases.

In the case of discrepant views on causality between the investigator and others, all parties will discuss the case. In the event that no agreement is made, the MHRA will be informed of both points of view.

| Relationship | Description |
|------------------|---|
| Unrelated | There is no evidence of any causal relationship |
| Unlikely | There is little evidence to suggest there is a causal relationship (e.g. the event did not occur within a reasonable time after administration of the trial medication). There is another reasonable explanation for the event (e.g. the participant's clinical condition, other concomitant treatment). |
| Possible | There is some evidence to suggest a causal relationship (e.g. because the event occurs within a reasonable time after administration of the trial medication). However, the influence of other factors may have contributed to the event (e.g. the participant's clinical condition, other concomitant treatments). |

| | |
|-----------------------|--|
| Probable | There is evidence to suggest a causal relationship and the influence of other factors is unlikely. |
| Definitely | There is clear evidence to suggest a causal relationship and other possible contributing factors can be ruled out. |
| Not assessable | There is insufficient or incomplete evidence to make a clinical judgement of the causal relationship. |

6.3 Reporting Procedures

All adverse events should be reported. Depending on the nature of the event the reporting procedures below should be followed. Any questions concerning adverse event reporting should be directed to the study coordination centre in the first instance. A flowchart is given below to aid in the reporting procedures.

6.3.1 Non serious AR/AEs

All such toxicities, whether expected or not, should be recorded in the toxicity section of the relevant case report form and sent to the study coordination centre within one month of the form being due.

6.3.2 Serious AR/AEs

Fatal or life threatening SAEs and SUSARs should be reported on the day that the local site is aware of the event. The SAE form asks for nature of event, date of onset, severity, corrective therapies given, outcome and causality (i.e. unrelated, unlikely, possible, probably, definitely). The responsible investigator should sign the causality of the event. Additional information should be sent within 5 days if the reaction has not resolved at the time of reporting.

SAEs

An SAE form should be completed and faxed to the study coordination centre for all SAEs within 24 hours. However, relapse and death due to a non study drug related condition and hospitalisations for elective treatment of a pre-existing condition do not need reporting as SAEs.

SUSARs

In the case of suspected unexpected serious adverse reactions, the staff at the site should:

Complete the SAE case report form & send it immediately (within 24 hours,), signed and dated to the study coordination centre together with relevant treatment forms and anonymised copies of all relevant investigations

Or

Contact the study coordination centre by phone and then send the completed SAE form to the study coordination centre within the following 24 hours as above.

The study coordination centre will notify the MHRA, REC, the Sponsor and the Funder (Incyte: [contact] or via fax to [name]) of all SUSARs and SAEs occurring during the study according to the following timelines; fatal and life-threatening within 7 days of notification and non-life threatening within 15 days. All investigators will be informed of all SUSARs occurring throughout the study.

Local investigators should report any SUSARs and /or SAEs as required by their Local Research Ethics Committee and/or Research & Development Office

6.3.3 Procedures for Reporting SAEs and Exposure to Study Drug During Pregnancy to the Funder, Incyte

As the Study is **interventional**, the Institution must report to Incyte the following, regardless of the Principal Investigator's causality assessment:

- i. all Serious Adverse Events (SAEs), and
- ii. Information regarding exposure to the Study Drug during pregnancy.
- a. Initial Reporting:
 - iii. Upon learning of an SAE or exposure to Study Drug during pregnancy that is required to be reported pursuant to Applicable Law, Institution shall complete and submit the Adverse Event Report Form or Pregnancy report form, as applicable, to Incyte within twenty-four (**24**) hours of learning of the event, via email to [contact] or via fax to [name].
 - iv. If critical or outstanding information is missing from the Adverse Event (or Pregnancy) Report Form or additional clarification is needed, Incyte shall submit a Data Clarification Form ("DCF") to the Institution/Principal investigator. In any case, Institution shall be solely responsible to respect of pharmacovigilance obligations and as such, will be the sole decision-making entity in case of disagreement.
- b. Follow-up Reporting:
 - i. When new information regarding an initially reported SAE or exposure to Study Drug during pregnancy becomes available, the Institution shall provide such follow-up information on a new or updated Adverse Event (or Pregnancy) Report Form within twenty four (24) hours of becoming aware of the information, via email to [contact] or via fax to [name].

Contact details for reporting SAEs and SUSARs

[contact]

attention [name]

Please send SAE forms to: [contact]

[contact] (Mon to Fri 09.00 – 17.00)

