7.2.1 Analysis Plan

Due to sample size constraints, for the primary outcomes of assessing the safety and tolerability of Itacitinib and overall response rate, we will use descriptive measures such as frequencies and percentages.

All patients who receive at least one dose of study treatment will be included in the safety analysis set. The frequency of adverse events (AEs) will be assessed for severity (NCI CTCAE v4.03), expectedness, seriousness and causal relationship to study drugs(s). In addition, AEs will be summarised by toxicity type, impact on study drug(s) and by timing.

All efficacy data in the study will be analysed on an intention-to-treat (ITT) basis, regardless of treatment received. To be considered 'evaluable' for the primary efficacy analysis, a patient must have a week 8 tumour assessment or evidence of disease progression or death prior to week 8.

For quality of life measures, both means and standard deviations for continuous variables as well as frequencies and percentages for categorical variables will be used.

For the translational / exploratory endpoints, appropriate descriptive measures as well as univariate models will be shown as dependent on whether the relevant measure is categorical or continuous, whether the test is paired or not and whether is it normally or non-normally distributed as indicated below. Translational endpoints may not be included in the Clinical Study Report.

Univariate models will be performed for all demographic and other study variables, as statistically appropriate, as well as to test for confounding due to sample size constraints, with models such as Fisher's exact test or the Chi-square test utilised for categorical variables and t-tests or the Wilcoxon test (if the continuous variable does not follow a normal distribution) for continuous ones. For all estimates, 95% confidence intervals will be calculated.

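### Section 6.3.2 exempts deaths attributed to a non-drug cause from SAE reporting, which conflicts with its own rule for fatal SAEs and with the funder rule in 6.3.3

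*Combined protocol and SAP*

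**What the plan says.** Five parts of the combined protocol and SAP bear on the point.

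- **Definition (6.1).** An SAE is "any untoward medical occurrence or effect that at any dose" meets one of the listed criteria, the first of which is "Results in death". No causality condition is attached.
- **Site reporting (6.3.2).** "Fatal or life threatening SAEs and SUSARs should be reported on the day that the local site is aware of the event". The general rule follows: "An SAE form should be completed and faxed to the study coordination centre for all SAEs within 24 hours". The next sentence makes an exception to SAE reporting: "relapse and death due to a non study drug related condition and hospitalisations for elective treatment of a pre-existing condition do not need reporting".
- **Funder reporting (6.3.3).** "the Institution must report to Incyte the following, regardless of the Principal Investigator's causality assessment", and the first item listed is all SAEs. The step that sets the 24-hour deadline is worded for events reportable under Applicable Law; the lead requirement has no such limit.
- **Causality (6.1 and 6.2).** The treating investigator assigns causality on a six-level scale. Section 6.1 lets either the investigator or the sponsor judge an event related. Section 6.2 sends doubtful cases to the coordination centre and tells the MHRA of unresolved disagreement.
- **Analysis (2.1 and 7.2.1).** The primary safety endpoint is adverse events graded by CTCAE. In the analysis, "The frequency of adverse events (AEs) will be assessed for severity (NCI CTCAE v4.03), expectedness, seriousness and causal relationship to study drugs(s").

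**The concern.** The exemption covers death from any condition held to be unrelated to the drug, not only progression of the cancer. Someone must decide relatedness before the site knows whether an SAE form is due, and that person is the treating investigator. If the answer is unrelated, no form is required, and the coordination centre and sponsor may have nothing on which to form their own view.

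Attribution is hard in this population. Patients have advanced HCC, and the inclusion criteria (3.3.1) admit Child-Pugh B7. Section 1.4.2 says the drug acts on the immune system, and 1.2.3 warns of a possible increase in infections. Section 1.2.3 also lists pneumonia and gastrointestinal haemorrhage among the SAEs seen on monotherapy. A death from either could readily be put down to the underlying liver disease.

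Safety and tolerability is one of the two primary outcomes, and the only numerical stopping rule in 7.1 concerns zero responses. Safety oversight therefore rests on complete individual reports.

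**Working it through.** No sample size, power or alpha depends on this point, and the plan gives no figure to reproduce. The check is mainly a comparison of rules.

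**Step 1. Apply each rule to one case:** a patient on treatment dies, and the investigator rates the death unrelated.

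| Rule | Is the death reported as an SAE? |
|---|---|
| 6.1 definition | It meets the definition, whatever the cause |
| 6.3.2, fatal SAEs | Yes, the same day |
| 6.3.2, all SAEs | Yes, within 24 hours |
| 6.3.2, exemption | No |
| 6.3.3, funder | Yes, irrespective of causality; the 24-hour step applies if reportable under Applicable Law |

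A site following the exemption and a site following 6.3.3 would act differently on the same death.

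**Step 2. Check the exemption against the causality scale.** The SAE form described in 6.3.2 offers *unrelated* and *unlikely* as answers, so unrelated SAEs were expected to arrive on it. The scale in 6.2 has six levels, and the exemption is not tied to any of them. It does not say whether a death rated *unlikely* or *not assessable* is exempt.

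**Step 3. Follow the second opinion.** The sponsor's judgement (6.1), the discrepant-views process (6.2) and the coordination centre's onward notification of fatal events within 7 days (6.3.2) all depend on the centre learning of the event. Under the exemption, no SAE form need reach it.

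**Step 4. Look for another recording route.** Section 6.3 says that every AE is to be reported. The CRF toxicity route in 6.3.1 is headed for non-serious events, and 6.3.2 describes the SAE form. No route is written for an event that is serious but exempt. Section 6.3 mentions a flowchart that is not in the text available for this review; it may or may not fill this gap.

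**Step 5. Illustrate the size.** Assume 25 treated patients (3.1, 7.1). The documents give no expected number of deaths, so a range is shown. The proportion is x/25. The exact (Clopper-Pearson) limits are:

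- lower = Beta quantile at 0.025 with parameters x and 25 − x + 1
- upper = Beta quantile at 0.975 with parameters x + 1 and 25 − x

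| Deaths x | x/25 | Exact 95% CI |
|---|---|---|
| 0 | 0% | 0% to 13.7% |
| 1 | 4% | 0.1% to 20.4% |
| 2 | 8% | 1.0% to 26.0% |
| 3 | 12% | 2.5% to 31.2% |
| 4 | 16% | 4.5% to 36.1% |
| 5 | 20% | 6.8% to 40.7% |

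For x = 0 the upper limit is 1 − 0.025^(1/25) = 0.137. Each omitted death moves the estimate by 1/25 = 4 percentage points. If two deaths occurred and both were left out, the table would show the first row instead of the third.

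**The case against.** The strongest reply is that a definition and a reporting rule do different jobs. Section 6.1 says what is serious; 6.3.2 says what must be sent in, and its wording marks a deliberate exception. The elective-hospitalisation exemption departs from 6.1 in the same way and troubles nobody. This largely stands, so the tension with 6.1 is the weakest part of the point. It does not answer the conflict with the fatal-SAE rule or with 6.3.3. The Applicable Law qualifier in 6.3.3 softens the funder deadline but not the lead requirement.

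There are also safeguards. A non-elective admission or life-threatening episode before death stays reportable whatever its cause, and doubt about causality goes to the coordination centre. The first helps only where such an episode came before the death; the second only where the site has doubts.

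A reader might go further and infer three things that the documents do not support.

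- *That the exemption removes deaths from the primary safety endpoint and so biases it downward.* The endpoint is all AEs by CTCAE. AEs are defined without regard to relatedness, 6.3 asks for all of them, and 7.2.1 uses causality as a tabulation field, not a filter. The exemption concerns reporting as SAEs only.
- *That deaths are withheld from the steering committee.* Section 7.1 has it reviewing safety and clinical information every 6 months, and nothing limits it to SAE forms. OS and PFS (2.2) both count all-cause death.
- *That lack of blinding is the problem.* In a single-arm trial there is no allocation to conceal. The issue is that one person's judgement acts as the gate.

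**Conclusion.** The point holds as an internal conflict in the reporting rules, with a risk of omission attached. Two rules in 6.3.2 contradict each other for deaths judged unrelated, and the exemption also contradicts 6.3.3. As written, a single attribution at the site can keep a fatal event from the sponsor's causality review. No recording route is written for such an event, so the seriousness and causality tables in 7.2.1 may miss it. OS would still count the death, but it neither shows causality nor supplies a prompt individual report.

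The size cannot be estimated from the documents. The 4 points per death, and the shift from 8% to 0% for two deaths, are illustrations. They assume 25 treated patients and that the omitted deaths are absent from the AE data as well as from the SAE forms, which the text permits by silence but does not direct. The reading of the recording gap also assumes that the flowchart mentioned in 6.3 does not close it. This should be corrected; it does not affect the efficacy design.

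**What to change.** - Remove death from the exemption in 6.3.2 and reconcile that section with 6.1 and 6.3.3. The exemption for elective hospitalisation can stay.
- State that every death from first dose to the 28-day safety follow-up visit (3.4.1) is reported as an SAE irrespective of causality. Use the same-day timeline that 6.3.2 already sets for fatal SAEs; a separate 24-hour limit for deaths would create a new inconsistency.
- Record the cause of death, including disease progression, as a field on the form, so that attribution becomes data and not an entry condition.
- State in 7.2.1 that all such deaths appear in the safety tables, by cause and by causality rating.

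The cost is a wording change and a few additional SAE forms, including forms for progression deaths. With about 25 patients that burden is small.

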7 STATISTICAL CONSIDERATIONS

7.1 Sample Size and Power Calculation

This is a single arm phase Ib pilot study to evaluate the effect of Itacitinib in 25 patients with advanced HCC. The two primary outcomes for this study are safety and tolerability as well as overall response rate. The study will be powered on overall response rate as per the below. A trials steering committee will convene every 6 months to review safety and clinical data.

The Simon's minimax two-stage design will be used where the null hypothesis that the clinical benefit rate (CBR) is 0.05 will be tested against a one-sided alternative, defining the maximum unacceptable activity (p_0) for the experimental treatment as an overall response rate of 5% (33,34). Assuming the experimental treatment is able to achieve a minimal acceptable activity (p_1) of at least 25% of overall response rate so that the null hypothesis can be rejected, i.e. to test the alternative one-sided hypothesis with 90% power that the overall response rate (p_1) is greater than p_0 , at least 4 or more response patients with clinical benefit will have to be reported among the final sample size of 25 patients. In accordance with the Simon's minimax two-stage design, an interim comparison of activity will be conducted in the first stage at complete assessment of the primary efficacy endpoint for the first 15 patients accrued. For a 20% difference in response rate CBR (5% v 25%), at least 1 patient with overall response should have been observed among the first 15 patients. If there are 0 responses in these 15 patients, the study will be stopped. Otherwise, 10 additional patients will be accrued for a total of 25 and a second comparison will be made on the final sample size. This design yields a one sided type I error rate of 0.05 and power of 0.90 when the true response rate is 0.25.

7.2 Analysis Plan

The clinical data will be entered and stored in InForm™ database. Statistical analysis will be conducted using R version 3.0.1 and Stata version 14.

One interim analysis is planned as described above for the efficacy primary endpoint. A final analysis will be conducted at the end of the study. Analyses will include an intent to treat analysis including all patients enrolled and a per protocol analysis using all patients who complete the study without major protocol violations.

Histograms and boxplots will be used to check the distribution and possible outliers for continuous variables. Continuous variables that follow a normal distribution will be summarised using means and standard deviations. Skewed continuous variables will be summarised using medians and inter-quartile ranges. Categorical variables will be summarised using frequencies and percentages.

A separate statistical analysis plan will be prepared and finalised prior to database lock. Any deviation(s) from the final statistical plan in the final analysis will be described and justification will be given in the final report.

7.2.1 Analysis Plan

Due to sample size constraints, for the primary outcomes of assessing the safety and tolerability of Itacitinib and overall response rate, we will use descriptive measures such as frequencies and percentages.

All patients who receive at least one dose of study treatment will be included in the safety analysis set. The frequency of adverse events (AEs) will be assessed for severity (NCI CTCAE v4.03), expectedness, seriousness and causal relationship to study drugs(s). In addition, AEs will be summarised by toxicity type, impact on study drug(s) and by timing.

All efficacy data in the study will be analysed on an intention-to-treat (ITT) basis, regardless of treatment received. To be considered 'evaluable' for the primary efficacy analysis, a patient must have a week 8 tumour assessment or evidence of disease progression or death prior to week 8.

For quality of life measures, both means and standard deviations for continuous variables as well as frequencies and percentages for categorical variables will be used.

For the translational / exploratory endpoints, appropriate descriptive measures as well as univariate models will be shown as dependent on whether the relevant measure is categorical or continuous, whether the test is paired or not and whether is it normally or non-normally distributed as indicated below. Translational endpoints may not be included in the Clinical Study Report.

Univariate models will be performed for all demographic and other study variables, as statistically appropriate, as well as to test for confounding due to sample size constraints, with models such as Fisher's exact test or the Chi-square test utilised for categorical variables and t-tests or the Wilcoxon test (if the continuous variable does not follow a normal distribution) for continuous ones. For all estimates, 95% confidence intervals will be calculated.

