8.3 Consent

Consent to enter the study must be sought from each participant only after a full explanation has been given, an information leaflet offered and time allowed for consideration. Signed participant consent should be obtained. The right of the participant to refuse to participate without giving reasons must be respected. After the participant has entered the trial the clinician remains free to give alternative treatment to that specified in the protocol at any stage if he/she feels it is in the participant's best interest, but the reasons for doing so should be recorded. In these cases the participants remain within the study for the purposes of follow-up and data analysis. All participants are free to withdraw at any time from the protocol treatment without giving reasons and without prejudicing further treatment.

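### No rule stops a week-8 response that follows non-protocol anticancer therapy from counting as an itacitinib response; few patients are likely to be affected, and a short scoring rule would close the gap

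*Combined protocol and SAP*

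**What the plan says.** Section 7.2.1 sets the efficacy analysis: "All efficacy data in the study will be analysed on an intention-to-treat (ITT) basis, regardless of treatment received". A patient is evaluable for the primary efficacy analysis with a week-8 tumour assessment, or with progression or death before then. No condition concerns other treatment.

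Section 8.3 says that after entry "the clinician remains free to give alternative treatment to that specified in the protocol at any stage" if this is judged to be in the participant's interest, with the reasons recorded. It adds: "In these cases the participants remain within the study for the purposes of follow-up and data analysis".

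Section 5.2 lists as prohibited: "Use of any concurrent anticancer therapy (eg, chemotherapy, radiation therapy, surgery, immunotherapy, biologic therapy, hormonal therapy, or tumor embolization", apart from therapy that the protocol itself specifies.

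Section 7.1 sets the decision rule as a Simon two-stage design with a null response rate of 5% and a "minimal acceptable activity (p_1) of at least 25% of overall response rate". On the first stage it says: "If there are 0 responses in these 15 patients, the study will be stopped". Success needs at least 4 responders among 25. The claimed properties are: "This design yields a one sided type I error rate of 0.05 and power of 0.90 when the true response rate is 0.25".

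Four other places bear on the point:
- Section 4.2.1 has a patient leave the study after a treatment break of more than 14 days.
- The notes to Table 1 (section 3.4.1) schedule scans every 8 weeks until progression or withdrawal.
- Section 5 has concomitant treatments recorded in the CRF.
- Section 7.2 adds a per-protocol analysis that excludes major protocol violations, without defining them, and promises a separate statistical analysis plan before database lock.

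**The concern.** Ignoring what treatment was actually taken is usually the cautious choice in a randomised comparison, because both arms are handled alike. This trial has no second arm. The response count is set against a fixed 5% benchmark for itacitinib, so the activity of any other therapy given before the week-8 scan adds to the count and nothing offsets it. The error can only favour the drug.

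The decision counts are small. One response lets the trial pass stage 1 and four make it a success, so a single misattributed response matters. The plan neither says that such a response is excluded nor says that it is deliberately included. As written, it is included.

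**Working it through.** **Inputs.** Section 7.1 gives n1 = 15 (stop on 0 responses), n = 25, success at 4 or more, p0 = 0.05 and p1 = 0.25. The documents do not give two further quantities, so both are assumed:
- f, the share of patients who start other anticancer therapy before the week-8 scan and are still scanned: 4% to 20% (4% is one patient in 25).
- q, the chance that such a patient is a responder at that scan: 10% to 30%.

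**Step 1: reproduce the plan's figures.** The probability of success at response rate p is

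S(p) = Σ (x = 1 to 15) C(15,x) p^x (1−p)^(15−x) × P[Bin(10,p) ≥ 4−x].

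At p = 0.05:
- x = 1: 0.3658 × 0.0115 = 0.0042
- x = 2: 0.1348 × 0.0861 = 0.0116
- x = 3: 0.0307 × 0.4013 = 0.0123
- x ≥ 4: 0.0055
- Total: 0.0336

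At p = 0.25 the same four terms are 0.0317 + 0.1179 + 0.2125 + 0.5387 = 0.901. The chance of stopping at stage 1 under the null is 0.95^15 = 0.463. The plan's claims hold. An exact error of 0.034 against a stated 0.05 comes from the discreteness of the counts and is not a fault.

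**Step 2: one response certain to come from other therapy, true itacitinib rate 5%.** This step needs no switching rate.
- In stage 1 the trial can no longer stop, and 3 more responses are needed from 24 patients: P[Bin(24, 0.05) ≥ 3] = 0.116.
- In stage 2: Σ (x = 1 to 15) C(15,x) 0.05^x 0.95^(15−x) × P[Bin(9, 0.05) ≥ 3−x] = 0.112.

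**Step 3: a range of assumed rates.** If switched patients respond at q instead of 5%, the effective rate is p = (1−f) × 0.05 + f × q. For example, f = 10% and q = 20% give 0.90 × 0.05 + 0.10 × 0.20 = 0.065, and S(0.065) = 0.075. False success is:

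| f | q = 10% | q = 20% | q = 30% |
|---|---|---|---|
| 4% | 0.038 | 0.048 | 0.059 |
| 5% | 0.039 | 0.052 | 0.067 |
| 10% | 0.045 | 0.075 | 0.112 |
| 20% | 0.059 | 0.133 | 0.234 |

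If switched patients also keep their 5% chance of responding to itacitinib, p = 0.05 + 0.95 × f × q. The two corners of the table then become 0.042 and 0.273, which is the same picture.

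**Step 4: the price of counting switched patients as non-responders.** This takes the worst case, in which none of them responded before switching, so the rate becomes p × (1−f).

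| f | False success, S(0.05(1−f)) | Power, S(0.25(1−f)) |
|---|---|---|
| 0 | 0.034 | 0.901 |
| 4% | 0.030 | 0.880 |
| 5% | 0.029 | 0.874 |
| 10% | 0.024 | 0.843 |
| 20% | 0.016 | 0.762 |

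**The case against.** The strongest reply is that the protocol's own schedule leaves few patients in this position. A reader might infer that someone who stops itacitinib at week 3, moves to another drug or has embolisation, and is scanned at week 8 would be credited to itacitinib. The documents do not support that as the normal course. Under section 4.2.1 the patient leaves the study once the break exceeds 14 days, so by about week 5 (3 + 2). Scheduled scans end at withdrawal. The safety visit, 28 days after the last dose and so at about week 7 (3 + 4), includes no tumour assessment. Without a week-8 scan, earlier progression or death, this patient is not evaluable.

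A reader might also infer that the protocol openly permits other anticancer therapy. It does not. Section 5.2 prohibits it when concurrent, and section 8.3 is a general consent clause that speaks of alternative treatment without mentioning anticancer therapy.

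Third, a reader might infer that PFS is clearly lengthened. Therapy given after progression cannot lengthen it, and scans stop at withdrawal, so the effect on PFS is limited.

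Most of this stands, and it narrows the point. What remains is therapy given while the patient is still on study, therapy started close to week 8, or an off-schedule scan. For these the safeguards do not settle the count:
- Section 5.2 covers concurrent therapy, so therapy begun after itacitinib stops is not clearly caught. Where section 5.2 is breached, section 7.2.1 still counts the result.
- The per-protocol analysis helps only if such therapy is a major violation, and the plan does not say whether treatment allowed under section 8.3 would be one.
- The separate analysis plan is due only before database lock, which may fall after the stage-1 decision.

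**Conclusion.** The point holds in a limited form. Sections 7.2.1 and 8.3 together let a week-8 response after non-protocol anticancer therapy count towards both decision rules, and sections 5.2 and 8.3 must be reconciled. The direction is known (in favour of the drug), but the size is not. One such response would raise false success from 0.034 to 0.112–0.116, more than twice the stated 0.05. Over the assumed ranges the figure runs from 0.038 to 0.234. It stays within 0.05 when switching is rare or the other therapy seldom produces a response by week 8, for example 0.048 at 4% switching with 20% response, and 0.045 at 10% with 10%. The upper end needs one patient in five to switch before week 8 and still be scanned, which the schedule makes unlikely.

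A reader might infer that the trial's error control has failed. The documents do not show this, because they give neither rate and the two-stage design itself is correct. This is a cheap improvement that removes an ambiguity and is not essential to the trial's validity.

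**What to change.** In section 7.2.1, for the primary endpoint:
- Count a response only if it is documented before any non-protocol anticancer therapy (systemic, locoregional, radiotherapy or surgery).
- Keep a patient who starts such therapy before week 8 without a documented response in the denominator, as a non-responder.
- Amend the evaluability sentence to match, so that such a patient does not drop out for want of a week-8 scan.

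Also state whether such therapy is a major protocol violation for the per-protocol analysis, report how many patients are affected, and reconcile sections 5.2 and 8.3. The scoring rule leaves clinicians' treatment decisions alone. Set it before the stage-1 count, since choosing it after seeing responses would compromise that decision. A PFS sensitivity analysis for new anticancer therapy is optional.

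The cost is a few sentences. Section 5 already has concomitant treatments recorded, so little new data is needed, and no patients or visits are added. The reported response rate may be slightly lower, and there is the loss of power shown in step 4, which is small if switching is rare.
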